9.4.5. Adherence and Retention Analyses

The number and percentage of subjects who withdraw from the study, with primary reason, will be summarized.

9.4.6. Baseline Descriptive Statistics

Medical history, physical examination, demographics and baseline characteristics will be summarized and presented. Medical history will be presented by MedDRA SOC and PT, summarizing the proportion of subjects who have a condition noted. Results from the baseline physical examination will be summarized by body system as recorded in the eCRF.

9.4.7. Interim Analyses

There are no interim analyses planned for this study.

9.4.8. Tabulation of Individual Response Data

Individual efficacy and safety data will be tabulated as appropriate.

9.5. Sample Size Calculation

In the AVA study of teriparatide and denosumab ([Dempster, 2016](#)), the mean (\pm SD) change from baseline in cancellous MS/BS (%) for teriparatide was 13.90 (\pm 9.38) at 3 months. In the ACTIVE study, the median % change from baseline in s-PINP at 3 months was 60% for abaloparatide and 94% for teriparatide. The ratio between the 2 groups is approximately 2/3 (= 60%/94%).

Using the same ratio and the results for teriparatide obtained from the AVA study, we can assume that the mean change from baseline in cancellous MS/BS (%) for abaloparatide at 3 months will be 9.2% (= 13.90*2/3). Assuming a standard deviation (SD) of 12.0%, a sample size of 21 completers will provide at least 90% power to detect a statistically significant change from baseline in cancellous MS/BS (%) for abaloparatide at 3 months of 9.2%. The study is planned to enroll approximately 25 subjects to accommodate a drop-out rate of 15%, including those with non-evaluable bone biopsy. Additional subjects may be enrolled if the number of evaluable biopsies is insufficient to achieve this power.

9.6. Measures to Minimize Bias

Not applicable.

9.7. Enrollment/Randomization/Masking Procedures

Not applicable.

10. ADMINISTRATIVE REQUIREMENTS

10.1. Ethical Considerations

This clinical study will be conducted in accordance with the current version of ICH Harmonized Tripartite Guidelines for Good Clinical Practice (GCP), with applicable local laws and regulations, and with the ethical principles laid down in the Declaration of Helsinki.

The Investigator will ensure that this study is conducted in full conformity with Regulations for the Protection of Human Subjects of Research codified in 21 CFR Part 50, 21 CFR Part 54, 21 CFR Part 56, 21 CFR Part 312, 21 CFR Part 314, and ICH GCP E6.

The IRB will review all appropriate study documentation to safeguard the rights, safety, and well-being of the subjects. The study will only be conducted at sites where IRB approval has been obtained. The protocol, IB, ICF, advertisements (if applicable), written information given to the subjects, safety updates, annual progress reports, and any revisions to these documents will be provided to the IRB by the Investigator or RADIUS or designee, as allowable by local applicable laws and regulations.

10.2. Subject Information and Informed Consent

The Investigator is responsible for obtaining written, informed consent from each subject interested in participating in this study before conducting any study-related procedures.

Written informed consent should be obtained after adequate, thorough, and clear explanation of the study objectives, procedures, as well as the potential hazards of the study. The method of obtaining and documenting the informed consent and the contents of the consent will comply with ICH GCP and all applicable laws and regulations and will be subject to approval by RADIUS or its designee.

10.3. Investigator Compliance

No modifications to the protocol should be made without the approval of both the Investigator and RADIUS. Changes that significantly affect the safety of the subjects, the scope of the investigation, or the scientific quality of the study (ie, efficacy assessments) will require IRB notification before implementation, except where the modification is necessary to eliminate an apparent immediate hazard to human subjects. RADIUS will submit all protocol modifications to the required regulatory authorities.

When circumstances require an immediate departure from procedures set forth in the protocol, the Investigator will contact RADIUS to discuss the planned course of action. If possible, contact should be made before the implementation of any changes. Any departures from protocol must be fully documented in the source documentation.

10.4. Access to Records

The Investigator must make the office and/or hospital records of subjects enrolled in this study available for review by site monitors at the time of each monitoring visit, audit by RADIUS QA and inspection by the regulatory agencies. The records must also be available for inspection, verification, and copying, as required by applicable laws and regulations, by officials of the regulatory health authorities (FDA and others). The Investigator must comply with applicable privacy and security laws for use and disclosure of information related to the research set forth in this protocol.

10.5. Subject Data Confidentiality

To maintain subject confidentiality, all eCRFs, study reports and communications relating to the study will identify subjects by assigned subject numbers. As required by federal regulations, the Investigator will allow RADIUS and/or its representatives access to all pertinent medical records to allow for the verification of data gathered in the eCRFs/SAE Forms and the review of the data collection process. The FDA (or other regulatory authority) may also request access to all study records, including source documentation, for inspection.

As applicable, in accordance with the Health Insurance Portability and Accountability Act (HIPAA) and associated privacy regulations, a subject authorization to use personally identifiable health information may be required from each subject before research activities begin.

Subject confidentiality is strictly held in trust by the participating Investigators, their staff, and RADIUS and their representatives. This confidentiality is extended to cover testing of biological samples and genetic tests in addition to the clinical information relating to participants. Therefore, the study protocol, documentation, data, and all other information generated will be held in strict confidence. No information concerning the study or the data will be released to any unauthorized third party without prior written approval of RADIUS.

10.6. Research Use of Stored Human Samples, Specimens, or Data

With the subject's approval, and as approved by the site's IRB, biological samples may be stored at a centralized facility determined by RADIUS. These samples could be used for retrospective biomarker research or analysis of clinical response to therapy. The storage facility will be provided with a code-link that will allow linking the biological specimens with the phenotypic data from each subject, maintaining the masking of the identity of the subject.

During the conduct of the study, any individual subject can choose to withdraw consent to have biological specimens stored for future research. When the study is completed, access to study data and/or samples will be provided through RADIUS.

10.7. Data Quality Assurance

RADIUS or its designated representative will conduct a study site visit to verify the qualifications of each Investigator, inspect clinical study site facilities as needed, and inform the Investigator of responsibilities and procedures for ensuring adequate and correct study documentation.

The Investigator is required to prepare and maintain adequate and accurate case histories designed to record all observations and other data pertinent to the study for each study subject. Study data for each enrolled subject will be entered into an eCRF by site personnel using a secure, validated web-based electronic data capture (EDC) application. RADIUS will have read-only access to all data upon entry in the EDC application.

Instances of missing, discrepant, or uninterpretable data will be queried with the Investigator for resolution. Any changes to study data will be made to the eCRF and documented in an audit trail, which will be maintained within the clinical database.

To ensure compliance with GCP and all applicable regulatory requirements, a quality assurance audit may be conducted. Regulatory agencies may also conduct a regulatory inspection of this study. Such audits/inspections can occur at any time during or after completion of the study. If an audit or inspection occurs, the Investigator and institution agree to allow the auditor/inspector direct access to all relevant documents and to allocate his/her time and the time of his/her staff to the auditor/inspector to discuss findings and any relevant issues. In the case of an audit or inspection, the Investigator or a delegate will alert RADIUS, as soon as he/she becomes aware of the audit or inspection.

The Investigator and study staff are responsible for maintaining a comprehensive and accurate filing system of all study-related documentation that will be suitable for inspection at any time by RADIUS, its designees, and/or regulatory agencies. In signing this protocol, the Investigator understands and agrees to give access to the necessary documentation and files.

10.8. Monitoring

RADIUS is responsible for ensuring the proper conduct of the study with regard to protocol adherence and validity of data recorded in the clinical database. The study will be monitored by RADIUS or its designee. Monitoring will be done by personal visits from a representative of RADIUS, or designee (site monitor), who will review the eCRFs, SAE Forms and source documents. The site monitor will ensure that the investigation is conducted according to the protocol design and regulatory requirements.

10.9. Data Collection and Management Responsibilities

Data collection is the responsibility of the clinical study staff at the site under the supervision of the Investigator. The Investigator is responsible for ensuring the accuracy, completeness, legibility, and timeliness of the data reported.

RADIUS will provide the study sites with secure access to and training on the EDC application sufficient to permit site personnel to enter and correct information in the eCRFs on the subjects for which they are responsible for.

An eCRF will be completed for each subject who receives at least one dose of study drug. It is the Investigator's responsibility to ensure the accuracy, completeness, clarity, and timeliness of the data reported in the subject's eCRF. Source documentation supporting the eCRF data should indicate the subject's participation in the study and should document the dates and details of study procedures, AEs, other observations, and subject status.

The Investigator, or designated representative, should complete the eCRF in a timely manner after information is collected.

The audit trail entry will show the user's identification information and the date and time of any correction. The Investigator must provide formal approval of all the information in the eCRFs, including any changes made to the eCRFs, to endorse the final submitted data for the subjects for whom the Investigator is responsible.

RADIUS will retain the eCRF data, queries and corresponding audit trail. A copy of the final archival eCRF in the form of a compact disc or other electronic media will be provided to the site for placement in the Investigator's study file.

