- ^k If the subject reports that a fracture has occurred, remind the subject to bring X-rays and any medical reports of the fracture to the next clinic visit. Documentation must be obtained on all new fractures that occur during the study. This documentation should be maintained in the source documents.
- ^l Subject will be instructed on completion of diary in the Pretreatment Period to include administration of medications for bone biopsy labeling procedure. The subject medication diary will be reviewed by study personnel at each study visit during the Treatment Period to ensure subject compliance.
- ^m AEs and SAEs will be recorded on the case report forms starting from the time of subject entry into the Screening Period (Visit 1) of the study (signed informed consent) until 30 days after the last dose of study medication. All AEs will be followed until resolution or stabilization. Any SAEs that occur at any time after completion of the study, which are considered by the Investigator to be related to study treatment, must be reported to the Sponsor or its designee.
- ⁿ Vitamin D supplements are required to be administered daily from the Pretreatment Period until the end of the Treatment Period. Calcium will also be administered daily, with the exception of the days of administration of demeclocycline and tetracycline where calcium administration will be withheld.

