8. ADVERSE EVENT AND SERIOUS ADVERSE EVENT DOCUMENTATION

8.1. Evaluation of Safety

Timely, accurate, and complete reporting and analysis of safety information from clinical studies are crucial for the protection of subjects and is mandated by Regulatory Agencies worldwide. All clinical studies sponsored by RADIUS will be conducted in accordance with Standard Operating Procedures (SOPs) that have been established to conform to regulatory requirements worldwide to ensure appropriate reporting of safety information.

All AEs are collected from the time of the informed consent until 30 days after last dose of investigational product. Where possible, a diagnosis rather than a list of symptoms should be recorded. All AEs should be captured on the appropriate AE pages in the eCRF and in source documents. The Investigator will assess all AEs and determine reporting requirements to the Sponsor as well as the IRB.

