8.1.3. Recording Adverse Events

All AEs/SAEs will be entered into the electronic database.

Planned hospital admissions or surgical procedures for an illness or disease that existed before the subject was enrolled in the study are not to be considered AEs unless they occur at a time other than the planned date or the pre-existing illness or disease worsens after enrollment into the study.

Fractures identified during the study are not to be recorded as AEs unless the subject is hospitalized, the fracture is complicated, or the Investigator considers the fracture to be unrelated to the subject’s underlying osteoporosis. All fractures will be identified and evaluated as part of the disease assessment and will be documented in the case report form and by collection of source documents.

For both serious and non-serious adverse events, the Investigator must determine the intensity of the event and the relationship of the event to study drug administration. Intensity for each AE will be defined according to the following criteria:

Intensity	Definition
Mild	Awareness of sign or symptom, but easily tolerated.
Moderate	Discomfort enough to cause interference with normal daily activities.
Severe	Inability to perform normal daily activities.

If the intensity of an adverse event changes within a day, the maximum intensity should be recorded. If the intensity changes over a longer period of time, the changes should be recorded as separate events (having separate onset and stop dates for each intensity).

Relationship to blinded study drug administration will be determined by the Investigator according to the following criteria:

Relationship	Definition
None	No relationship between the event and the administration of study drug. The event is related to other etiologies, such as concomitant medications or subject's clinical state.
Unlikely	The current state of knowledge indicates that a relationship to study drug is unlikely or the temporal relationship is such that study drug would not have had any reasonable association with the observed event.
Possible	A reaction that follows a plausible temporal sequence from administration of the study drug and follows a known response pattern to the suspected study drug. The reaction might have been produced by the subject's clinical state or other modes of therapy administered to the subject.

Relationship	Definition

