9.4.4. Safety Analyses

Unless otherwise specified, safety analyses will be conducted using the Safety Population and will be descriptive in nature.

Study drug exposure and study drug compliance will be calculated. The duration of study drug exposure, total dose received, and percent compliance will be summarized.

All AEs will be coded using MedDRA. The number and percent of subjects who experienced treatment-emergent AEs (TEAEs) will be summarized by MedDRA system organ class (SOC), and preferred term (PT). Summaries will also be provided for severe TEAEs, serious TEAEs (SAEs), TEAEs leading to study drug withdrawal, drug-related TEAEs (with probable or possible relationship to study drug), and TEAEs by maximum severity (mild, moderate, severe).

The number and percent of subjects who report TEAEs associated with hypercalcemia and hypercalciuria will be summarized.

All AEs collected prior to the first dose of study drug will be summarized separately.

Descriptive statistics for clinical laboratory data (including serum calcium and albumin), vital signs (including blood pressure), ECGs, and Investigator assessment of local tolerance will be provided by visit. For laboratory data, vital signs and ECGs, absolute results and changes from baseline will be presented. In addition, laboratory test results will be classified as above normal limit, within normal limit, or below normal limit. Laboratory shift frequencies will be tabulated between the Screening visit and relevant post-baseline visit(s).

Concomitant medications will be coded using the WHO Drug Dictionary and summarized by number and percentage of subjects using each class and preferred drug term.

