## **4.7 Safety Analyses**

All safety analyses will be conducted using the Safety population. Unless otherwise specified, no formal statistical hypothesis testing will be performed for safety endpoints, and the presentations will be based on descriptive summaries.

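### Protocol 10.9 conflicts with the rules for recording adverse events from consent, and the SAP leaves subjects who took demeclocycline but never abaloparatide out of every adverse event table

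*Protocol*

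**What the plan says.** Protocol 10.9 sets the eCRF rule by dosing: "An eCRF will be completed for each subject who receives at least one dose of study drug". Study drug here is abaloparatide (Protocol 6.4), first given on Day 1.

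Four other places set a rule without a dosing condition:

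- Protocol 8.1 on timing: "All AEs are collected from the time of the informed consent until 30 days after last dose of investigational product". The same section on where events go: "All AEs should be captured on the appropriate AE pages in the eCRF and in source documents".
- Protocol 8.1.3: "All AEs/SAEs will be entered into the electronic database".
- Protocol Table 1, footnote m, starts recording on the case report form at Visit 1, once consent is signed.
- Protocol 10.7: "Study data for each enrolled subject will be entered into an eCRF by site personnel".

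On analysis, Protocol 9.4.4 states: "All AEs collected prior to the first dose of study drug will be summarized separately". The synopsis makes the same commitment. SAP 4.7 states: "All safety analyses will be conducted using the Safety population". SAP 2.1 defines that population as enrolled subjects with at least one dose of abaloparatide. SAP 4.7.1 plans a table of events that are not treatment-emergent and names no other population for it.

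**The concern.** The time before Day 1 is not passive screening. Under Protocol 7.2.6 every subject starts demeclocycline 18 days before Day 1, in two 3-day courses separated by 12 days. Known hypersensitivity to tetracyclines is an exclusion criterion, so the protocol itself recognizes that reactions are possible. A subject may take the label, have an adverse event, and for that reason never receive abaloparatide.

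Two things are at stake. First, sites have conflicting instructions on whether such a subject needs an eCRF. Second, the pre-dose adverse event table would be selective: it keeps subjects who got through labeling and drops those who stopped because of an event during it.

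**Working it through.** The check is mainly a comparison of the texts. Take one subject who consents, takes demeclocycline, has a non-serious adverse event and is never given abaloparatide.

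**Step 1. Is the event entered?**

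| Rule | Condition | Event entered? |
|---|---|---|
| Protocol 10.9 | at least one dose of study drug | eCRF not required |
| Protocol 8.1 | from consent | yes |
| Protocol 8.1.3 | none | yes |
| Protocol Table 1, footnote m | from Visit 1 | yes |
| Protocol 10.7 | enrolled | yes, if the subject counts as enrolled |

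The protocol does not define enrollment. For retested subjects, 7.2.5 counts the 30 days for safety laboratory results back from enrollment, while 7.5.1 counts them from Day 1. The reach of 10.7 is therefore unclear. The other three rules do not depend on that word. The result is a contradiction between 10.9 and the rest, not a uniform rule against entry.

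**Step 2. Does the event reach a table?** The opening of SAP Section 4 makes the Safety Population the default for all summary tables, and SAP 4.7 applies it to all safety analyses. The subject has had no abaloparatide, so the event is in no adverse event table, including the one for events that are not treatment-emergent. This is so even if the event was entered correctly. The demeclocycline exposure summary in SAP 4.3 falls under the same default.

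**Step 3. Does the event reach a listing?** Yes, if it was entered. SAP 3.2, 3.10 and 4.7.1 promise listings of all subject data, all available data and all adverse events.

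**Step 4. Is the narrowing declared?** SAP Section 5 lists five changes from the protocol. The population for pre-dose events is not among them.

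**Step 5. How many subjects?** The documents give no rate of loss between labeling and Day 1. The only related figure is the overall attrition allowance in Protocol 9.5, which reproduces: 21 / (1 − 0.15) = 24.7, rounded up to 25. That leaves 25 − 21 = 4 subjects, or 4/25 = 16%. The assumed range is therefore 0 to 4 of 25. The upper end puts all planned attrition before Day 1, although the allowance also covers later drop-outs and non-evaluable biopsies. Subjects lost before they count as enrolled would come on top.

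**Step 6. What is not affected?** The primary analysis uses the Bone-Biopsy Population. Treatment-emergent events, as SAP 4.7.1 defines them, require study drug to have started.

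**The case against.** A reader might infer that these events reach neither the database nor any output. The documents do not support that. Section 10.9 does not say that only dosed subjects get an eCRF. Three other places require entry of adverse events whatever the dosing status, and 10.7 requires data entry for every enrolled subject. Protocol 6.3 gives everyone who consents a subject number for use on the eCRFs, and 5.3.2 puts the reason for withdrawal on the case report form. Serious events go to the sponsor's pharmacovigilance group within 24 hours from the signing of consent (8.1.4). In a study of about 25 subjects, one more subject is easy to find in a listing.

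A reader might also infer that SAP 4.1 cannot report reasons for exclusion from the Safety Population. That follows only if 10.9 is read as exclusive. SAP 4.1 in fact points the other way, since it presupposes that data exist for enrolled subjects who were never dosed.

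Two further arguments concern the analysis. Protocol 9.4.4 opens with the Safety Population as its default, so its sentence on pre-dose events can be read within that default. And a safety population defined by abaloparatide suits a study of abaloparatide's safety; demeclocycline is described under concomitant medications.

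These arguments remove any claim of established data loss and support keeping the Safety Population for treatment-emergent events. They do not reconcile 10.9 with the other sections. Nor do they settle the pre-dose table: both protocol statements speak of all events before the first dose, neither names a population, and a listing is not a summary.

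**Conclusion.** The point holds in two limited parts.

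1. Protocol 10.9 contradicts 8.1, 8.1.3, 10.7 and footnote m of Table 1. The contradiction permits non-serious events of never-dosed subjects to go unentered. It does not show that any did.
2. Independently of the eCRF rule, SAP 4.7 keeps subjects who took demeclocycline but were never dosed out of every adverse event table. They appear at most in listings. This falls short of the protocol's commitment to summarize all pre-dose events, and the SAP does not list it as a change.

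The severity is minor. The number affected is an assumption, 0 to about 4 of 25, and zero is possible. The primary analysis and the treatment-emergent results do not change.

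**What to change.** - **Protocol 10.9:** align it with 8.1, 8.1.3, 10.7 and footnote m of Table 1, so that an eCRF with at least the adverse event and disposition pages is completed for every consented subject, or at minimum for every subject who takes demeclocycline.
- **SAP 4.7.1:** state that the pre-dose adverse event summary covers all subjects who took at least one dose of demeclocycline. Keep the Safety Population for treatment-emergent events.
- **If data collection has already ended:** confirm that labeled, never-dosed subjects have adverse event and disposition records, and produce the pre-dose table on the wider population.

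The cost is one sentence in each document, a few extra eCRFs, and one table whose denominator differs from that of the other safety tables and needs a footnote.
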